## III. APPROACH

We propose a two-center, randomized, double blind, placebo-controlled, parallel, three-episode, clinical trial of rizatriptan 10 mg oral tablets versus placebo for treating spontaneous vestibular attacks in patients with VM.

Our primary Specific Aim is to test hypotheses 1a-1d that rizatriptan will be:

- 1a. Superior to placebo in reducing the severity and duration of vestibular attacks as measured by:
  - (1) Proportion of treated attacks in which subjects experience a reduction in severity rating from Grade 3/2 to Grade 1/0 at one hour after taking study medication (see below for rating description). This is the main outcome measure; 1a(2)-1d(2) are secondary outcome measures.
  - (2) Proportion of treated attacks in which subjects achieve sustained relief (i.e., vestibular symptom severity rating of Grade 1/0) for 24 hours after taking study medication, without use of non-study therapies.
  - (3) Proportion of treated attacks in which subjects experience freedom from vestibular symptoms (i.e., severity rating of Grade 0) at one hour after taking study medication.
  - (4) Use of fewer non-study therapies after each attack treated with study medication.
- 1b. Superior to placebo in reducing severity of symptoms associated with vestibular attacks as measured by:
  - (1) Proportion of treated attacks in which subjects experience relief (reduction to Grade 1/0) from VM-associated symptoms (e.g., nausea, vomiting, motion sensitivity, gait disturbance, headache, photophobia, and phonophobia) at one hour after taking study medication.
  - (2) Proportion of treated attacks in which subjects achieve sustained relief from VM-associated symptoms for 24 hours after taking study medication without use of non-study therapies.
- 1c. Superior to placebo on treatment satisfaction and health-related quality of life as measured by:
  - (1) Scores on the Treatment Satisfaction Questionnaire for Medication (TSQM) at 48 hours after each attack treated with study medication
  - (2) Scores on the Short Form 12 (SF-12) at 48 hours after each attack treated with study medication
- 1d. Tolerated as well as placebo by patients with VM as measured by:
  - (1) No greater rate of treatment-emergent serious adverse events reported on the NCI Common Toxicity Criteria Scale 4.0^59 obtained 48 hours after each attack treated with study medication.

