**4. Treatment Phase.** Subjects who qualify for randomization will enter the Treatment Phase. They will be randomly assigned to parallel study arms in a 2:1 ratio of rizatriptan 10 mg encapsulated tablets or look-alike placebo capsules. Subjects will treat three vestibular attacks that manifest with Grade 3/2 vestibular symptoms. Associated symptoms, including headache, need not be present and may be of lesser severity. Headaches without vestibular symptoms are not eligible for study treatment, but may be treated in the subjects' usual manner. Subjects will be instructed to ingest one study capsule as soon as possible after onset of Grade 3/2 vestibular symptoms. They will record treatment response in their Vestibular Symptom Diaries by rating the severity of vestibular and associated symptoms at the time they take study medication and at 0.5, 1, 2, 4, 24, and 48 hours post-dose. Subjects will record adverse effects in accordance with the Common Toxicity Criteria Scale 4.0, treatment satisfaction on the TSQM, and quality of life on the SF-12 at 48 hours post-dose. Then they will contact study personnel by phone to review the attack and treatment response.

Subjects will treat one attack with study medication in a 48-hour period. Repeat dosing of study medication within 48 hours will not be permitted. Subjects must have a vertigo-free period of at least 48 hours before treating a subsequent vestibular attack with study medication. The relatively short plasma half-life of rizatriptan (2-2.5 hours) justifies the 48-hour wash out period. Subjects may use other medications to treat residual symptoms (see Concomitant Medications) but must wait at least 1 hour after taking the study medication. Additional treatments will be reported to study personnel together with other attack data. Subjects will remain in the Treatment Phase until they have treated three separate vestibular attacks, experience serious or intolerable adverse effects, withdraw for other reasons, or reach the end of the study. Study personnel will conduct telephone assessments on a monthly basis as they did during the Observation Phase. Extra visits to study clinics will be arranged as needed to re-evaluate subjects' health and treat problematic symptoms.

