**G. Concomitant Medications.** Subjects may use medications for migraine prophylaxis and comorbid medical conditions, although medication doses must be stabilized during the Observation Phase and remain unchanged for the entire Treatment Phase. Those who take triptans for migraine headaches can continue to use them but not within 48 hours of taking study medication for vertigo attacks during the Treatment Phase. Subjects may use symptomatic medications for relief of vertigo attacks during the Observation Phase and for relief of symptoms that remain after taking study medication during the Treatment Phase (starting 1 hour after taking the study medication so that the primary outcome measure is not affected). Subjects must discontinue monoamine oxidase inhibitors at least 3 months before randomization. Use of other antidepressants is permitted. Theoretical concerns about serotonin syndrome arising from concomitant use of SSRI or SNRI antidepressants and triptans have not been observed in investigations of concomitant medication use. These antidepressants will not be excluded, but subjects will be advised of potential adverse interactions.

**H. Safety Procedures.** Study personnel will be available during working hours and 24-hour emergency coverage will be provided at each site. Subjects who develop serious adverse events or medical conditions incompatible with safe use of rizatriptan will be withdrawn from the study. See Human Subjects for additional details.

**I. Data Management.** All data entry, data quality checking, data management, and statistical analyses will be conducted at the Data & Statistical Coordinating Center (DSCC) at UCLA under the direction of [name], who has extensive experience running DSCCs for clinical trials. The PI, Co-PI, and co-investigators will work with [name] to program questionnaires and data input forms (paper and electronic) as needed for the study. All members of the study staff will be trained in data collection and entry techniques prior to the start of the study. Strict rules and regulations for patient security and confidentiality will be implemented by the DSCC. All data transferred from each of the sites will be carefully checked and maintained, and the DSCC will ensure that both sites follow the data security procedures. These procedures will be incorporated into data handling protocols, and auditing principles and periodically checking will be used to ensure compliance.

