4. We will use this 3-step analysis procedure to test all outcome measures for hypotheses 1a-1d. However, the principal result of the study will be determined by the findings of bivariate analyses and multivariate modeling of the main outcome measure, 1.a.(1), plus favorable findings on tolerability measures, 1d(1)-1d(2). We will include all subjects who treat at least one vertigo attack with study drug (i.e., intent-to-treat analysis). A statistically significant result favoring rizatriptan over placebo on 1a(1) and absence of statistically significant differences on 1d(1)-1d(2) will support development of a Phase III clinical trial of rizatriptan for treating vestibular attacks in patients with VM. The design of future trials will also be informed by results of tests of secondary measures 1a(2)-1c(2). We did not hypothesize equal tolerability for rizatriptan and placebo, but rather an absence of significantly higher rates of serious adverse effects and drug-related treatment discontinuation, so our statistical analyses of measures 1d(1)-1d(2) will not include equivalence tests.

[figure not shown]

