#### **F. Subject Discontinuation**

An intent to treat approach will be used. All data acquired prior to termination for the reasons outlined below will be included in the primary analysis unless the subject withdraws consent. Every effort will be made to conduct a final study visit with subject upon withdrawal and subjects will be followed clinically until, if applicable, all adverse events resolve. The following events will result in subject discontinuation:

- Withdrawal of consent
- Withdrawal by the participant
- Withdrawal by the investigator  Intercurrent illness or event that precludes further visits to the study site or ability to evaluate disease

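### The primary outcome has no scoring rule for attacks medicated before one hour in breach of the protocol, so such an attack can count as a response to the study capsule.

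*Combined protocol and SAP*

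**What the plan says.** **Outcome.** Section III (Approach), item 1a(1), takes as the main outcome the share of treated attacks where "subjects experience a reduction in severity rating from Grade 3/2 to Grade 1/0 at one hour after taking study medication". No condition on other medication is attached. The 24-hour outcome, 1a(2), does carry one: relief must hold "for 24 hours after taking study medication, without use of non-study therapies".

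**Conduct.** Section III.D.4 (Treatment Phase) allows other medication for residual symptoms, but subjects "must wait at least 1 hour after taking the study medication". Section III.G (Concomitant Medications) repeats the restriction with its reason: "starting 1 hour after taking the study medication so that the primary outcome measure is not affected".

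**Data.** Section III.D.4 also states: "Additional treatments will be reported to study personnel together with other attack data". It does not ask for the time at which they were taken.

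**Analysis.** Section III.J.3, step 4, says: "We will include all subjects who treat at least one vertigo attack with study drug (i.e., intent-to-treat analysis". Section V.F adds: "All data acquired prior to termination for the reasons outlined below will be included in the primary analysis unless the subject withdraws consent". Neither place, nor the rest of III.J, says how 1a(1) is scored when the one-hour wait is not kept. The results summary at the end of the document repeats the outcome definition, again without a rescue condition.

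**The concern.** The plan treats medication in the first hour as a threat to the primary outcome, but guards against it only by an instruction to subjects. They treat Grade 2 or 3 vertigo without supervision, and section III.D.2 lets them use their usual treatments throughout the Observation Phase. Some breaches of the wait are foreseeable.

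When a breach happens, the written definition still gives a clear score: Grade 3/2 at dosing and Grade 1/0 at one hour is a response, whatever was taken in between. Relief from the other medication is then credited to the capsule. If rizatriptan works, the pressure to reach for something else is greater after placebo, so this credit would fall more often on the placebo arm and shrink the observed difference. The missing-data methods in III.J.3, step 6, do not help, because a rescued attack with a one-hour rating is not missing.

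**Working it through.** **1. Reproduce the planning figure.** Section III.J.1 gives 120 subjects at 2:1 (80 and 40), two-sided alpha 0.05, power 80%, and a detectable odds ratio of 3.2. The placebo rate behind that figure is not stated. I assume 22%, the placebo rate quoted there from the zolmitriptan trial and the only one given for vestibular migraine.

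- Active odds: 3.2 × 0.22/0.78 = 0.9026, so the active rate is 0.9026/1.9026 = 47.4%.
- Power formula: Φ[(p1 − p0 − 1.96 × SE0)/SE1], with SE0 from the pooled rate and SE1 from the separate rates.
- Pooled rate: (40 × 0.22 + 80 × 0.474)/120 = 0.390. SE0 = 0.0944 and SE1 = 0.0861.
- Power: Φ[(0.2544 − 0.1851)/0.0861] = Φ(0.805) = 79%.

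The plan's figure is reproduced to within about one point of power. It is not in dispute. Like the plan's own calculation appears to do, this one counts one response per subject.

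**2. Add early rescue.** The documents give no rate, so these inputs are assumptions:

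- a share e of all attacks in an arm is medicated before the one-hour rating;
- this happens only in attacks that would otherwise fail;
- a fraction q of those attacks reaches Grade 1/0 by one hour.

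Scored as rated, an arm's response rate is p + e × q. Scored with early rescue as non-response, it stays at p.

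Example with e = 10% on placebo, 5% on active, and q = 0.5:

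- Placebo: 0.22 + 0.10 × 0.5 = 0.270. Active: 0.474 + 0.05 × 0.5 = 0.499.
- Odds ratio: (0.499/0.501)/(0.270/0.730) = 2.70. Power 68%.

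| Early rescue, placebo / active | q | As rated, placebo vs active | Odds ratio | Power |
|---|---|---|---|---|
| none | – | 22.0% vs 47.4% | 3.20 | 79% |
| 5% / 5% | 0.5 | 24.5% vs 49.9% | 3.07 | 78% |
| 5% / 5% | 0.8 | 26.0% vs 51.4% | 3.01 | 77% |
| 10% / 5% | 0.5 | 27.0% vs 49.9% | 2.70 | 68% |
| 10% / 5% | 0.8 | 30.0% vs 51.4% | 2.47 | 61% |
| 10% / 5% | 0.2 | 24.0% vs 48.4% | 2.97 | 75% |
| 10% / 5% | 0.1 | 23.0% vs 47.9% | 3.08 | 77% |

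With early rescue scored as non-response, every row returns to 22.0% vs 47.4%, odds ratio 3.20, power 79%.

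**3. Relax the second assumption.** Suppose instead that early rescue strikes would-be responders and would-be failures alike, at 10% on placebo and 5% on active. Scoring it as non-response gives 0.22 × 0.90 = 19.8% and 0.474 × 0.95 = 45.1%, an odds ratio of 3.32. That is slightly above the 3.20 with no rescue, so the non-response rule can also overshoot. This is one reason to report the as-rated score beside it.

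**The case against.** **Early rescue is prohibited.** Two sections say so. The problem arises only through a protocol deviation, and a reader should not infer that the plan permits medication in the first hour. This stands. What remains open is the score for a deviating attack.

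**The contrast with 1a(2) proves little.** A reader might infer that the rescue condition was forgotten in 1a(1). The documents do not support that. The 24-hour outcomes cover hours in which other medication is allowed and so need the condition. The one-hour outcomes end when it becomes allowed, so a compliant attack does not. The pattern is consistent for compliant attacks.

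**The inputs are assumed.** No early-rescue rate, arm difference or rescue success rate is documented. Section III.L says that most subjects in a current trial at one site had been prescribed vestibular suppressants for acute attacks, and nothing shows that these relieve half of attacks in the rest of an hour. At 10-20% success the loss is small, as the last two rows of the table show. This also stands and limits the claim about size.

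**Scoring as rated is defensible.** It fits the stated intent-to-treat approach, and under the mechanism described the bias does not create a false positive. Much of the information is collected already: additional treatments are reported per attack, and use of non-study therapies is outcome 1a(4). Even so, as-rated scoring does not serve the aim that section III.G sets, that other medication should leave the primary outcome untouched. Keeping it as a sensitivity analysis preserves what is useful in it.

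**Conclusion.** The point holds in a limited form. As written, an attack medicated early against the protocol and rated Grade 1/0 at one hour is a response under 1a(1), contrary to the plan's own stated aim. The direction, towards no difference, depends on such deviations being commoner on placebo. The size is unknown. Under the stated assumptions it runs from minor (odds ratio 3.2 falling to about 3.0-3.1, power 77-78%, at 5% in both arms) to material (about 2.5-2.7, power 61-68%, at 10% versus 5% with 50-80% of rescues succeeding).

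A reader might go further and infer that early rescue explains why the results summary reports no difference on the primary outcome. The documents do not support that: they give no count of attacks medicated before one hour in either arm, so its influence can be neither shown nor excluded.

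This is a worthwhile, low-cost clarification of the outcome definition. It does not challenge the design or the sample size.

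**What to change.** - Add to 1a(1): a treated attack in which any non-study therapy was taken before the one-hour rating is a non-response.
- Record the clock time of any additional therapy and of the one-hour rating.
- Keep the as-rated score as a sensitivity analysis.
- Report the number of attacks with early rescue by arm.

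No change to the rescue rule is proposed.

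**Cost.** One sentence in the outcome definition and the clock times in the diary. Response rates become slightly lower, and some attacks that would have responded anyway are scored as failures. Under intact blinding, and if the drug has no effect, the rule should not favour either arm.

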**Table 2. Study Procedures and Rating Scales**

Procedures	Visit 1 Enrollment	Observation Phase	Visit 2 Randomization	Treatment Phase	Visit 3 End Point
Obtain informed consent	X				
Abstract medical record data	X				
Verify enrollment criteria	X				
Characterize baseline symptoms	X				
Instruct re Vestibular Symptom Diary	X		X		
Assess & stabilize comorbidity		1 st 3 months			
Review Vestibular Symptom Diary		Monthly	X	Monthly	X
Update health & medication list		Monthly	X	Monthly	X
Randomize for treatment			X		
Instruct re study treatment			X		
Dispense drug/placebo			X		
Treat 3 attacks				X	
Pregnancy Test			X		
Rating Scales					
Dizziness Handicap Inventory 	X		X		X
Anxiety Scale (GAD-7) 	X		X		X
Depression Scale (PHQ-9) 	X		X		X
Vestibular Symptom Diary		X		X	
Common Toxicity Criteria Scale 4.0 				X	
Treatment Satisfaction (TSQM) 				X	
Quality of Life Scale (SF-12) 	X		X	X	X
NEO-PI-3 Personality Inventory 	X				

**E. Outcome and Safety Measures (#1-4 mirror measures used in Phase III registration trials of rizatriptan)**

- 1. Vestibular Symptom Diary.** During Observation and Treatment Phases of the study, subjects will track the frequency of their headaches vestibular symptoms (unsteadiness/dizziness), and sensitivity to potential triggers of attacks (head/body motion, environmental stimuli, specific positions).
- 2. Common Toxicity Criteria Scale 4.0** (National Cancer Institute). A clinician-rated, comprehensive measure of toxicity from study medications in all body systems.
- 3. Treatment Satisfaction Questionnaire for Medication** (TSQM). A validated self-report measure of treatment satisfaction in four domains: effectiveness, side effects, convenience, and global satisfaction. Subjects will be asked whether they think they received rizatriptan or placebo after each dosing
- 4. Short Form 12** (SF-12). A 12-item self-report measure of health-related quality of life in six domains.
- 5. Dizziness Handicap Inventory** (DHI). A 25-item self-report of vertigo, dizziness, functional impairment, and emotional symptoms associated with vestibular symptoms.

6. **Generalized Anxiety Disorder Scale (GAD-7).** A 7-item self-report rating scale for anxiety, a common comorbidity of VM. The GAD-7 has cut-offs for clinically significant levels of anxiety symptoms.
7. **Patient Health Questionnaire (PHQ-9).** A 9 item self-report rating scale for depression, another common comorbidity of VM. The PHQ-9 has cut-offs for clinically significant levels of depressive symptoms.
8. **NEO-PI-3 Personality Inventory (NEO-PI-3).** A 240-item questionnaire that assesses traits of the Five Factor Model of personality (neuroticism, extraversion, openness, agreeableness, conscientiousness).

**F. Handling of Study Drug.** The Mayo Clinic Research Pharmacy will support both study sites. The research pharmacists will purchase rizatriptan 10 mg tablets from a commercial supplier. Unaltered rizatriptan tablets will be encapsulated. Look-alike lactose-containing placebo capsules will be manufactured in the Mayo Clinic Pharmacy Production Laboratory following Good Manufacturing Practices. For patients who are allergic to lactose, carboxymethyl cellulose will be used instead of lactose. All capsules will be labeled with NDC numbers so that active drug and placebo can be identified. Randomization codes will be entered into the Research Pharmacy record. When prescriptions for study drug are received from physician investigators, drug or placebo will be placed into prescription bottles with required labeling. Prescriptions will be verified and cross-checked against the Research Pharmacy record for each subject. Then the prescription will be dispensed to subjects or mailed to their homes. Subjects will return used and unused bottles to verify medication accuracy and adherence. Should any questions arise after study drug is dispensed, the research pharmacists will be able to identify study drug for each subject by cross referencing the NDC numbers and randomization codes. Research pharmacists will maintain drug logs and all other applicable regulatory paperwork.

**G. Concomitant Medications.** Subjects may use medications for migraine prophylaxis and comorbid medical conditions, although medication doses must be stabilized during the Observation Phase and remain unchanged for the entire Treatment Phase. Those who take triptans for migraine headaches can continue to use them but not within 48 hours of taking study medication for vertigo attacks during the Treatment Phase. Subjects may use symptomatic medications for relief of vertigo attacks during the Observation Phase and for relief of symptoms that remain after taking study medication during the Treatment Phase (starting 1 hour after taking the study medication so that the primary outcome measure is not affected). Subjects must discontinue monoamine oxidase inhibitors at least 3 months before randomization. Use of other antidepressants is permitted. Theoretical concerns about serotonin syndrome arising from concomitant use of SSRI or SNRI antidepressants and triptans have not been observed in investigations of concomitant medication use. These antidepressants will not be excluded, but subjects will be advised of potential adverse interactions.

**H. Safety Procedures.** Study personnel will be available during working hours and 24-hour emergency coverage will be provided at each site. Subjects who develop serious adverse events or medical conditions incompatible with safe use of rizatriptan will be withdrawn from the study. See Human Subjects for additional details.

**I. Data Management.** All data entry, data quality checking, data management, and statistical analyses will be conducted at the Data & Statistical Coordinating Center (DSCC) at UCLA under the direction of [name], who has extensive experience running DSCCs for clinical trials. The PI, Co-PI, and co-investigators will work with [name] to program questionnaires and data input forms (paper and electronic) as needed for the study. All members of the study staff will be trained in data collection and entry techniques prior to the start of the study. Strict rules and regulations for patient security and confidentiality will be implemented by the DSCC. All data transferred from each of the sites will be carefully checked and maintained, and the DSCC will ensure that both sites follow the data security procedures. These procedures will be incorporated into data handling protocols, and auditing principles and periodically checking will be used to ensure compliance.

We will use a reliable and secure system for data transfer. All survey and abstraction data will be transferred from each data sources to the DSCC through secured mechanisms (e.g., secured website, FTP or password protected files). All data sets will be stored in password protected folders on network server or password protected computers designated for use by the DSCC. We will monitor the data through serial evaluation of the databases and analytic products throughout the process. Any discrepancy and/or inconsistency in the data will be evaluated and corrected in a timely manner.

An analytical ID generated through a scramble function will be created for each individual patient to protect patient confidentiality. Data analyses conducted at the DSCC will use analytical files that contain only the encrypted analytical IDs; no other patient identifying information will be available. Standard labels and format libraries will be created to facilitate analysis. A codebook that contains the information about the standard variable names and coding system will be created.

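### Section III.F puts an NDC number on every capsule to tell active drug from placebo, and does not say that this number or the bottle label is kept from subjects and site staff

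*Combined protocol and SAP*

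**What the plan says.** The Approach section describes a "two-center, randomized, double blind, placebo-controlled, parallel, three-episode, clinical trial". Under Treatment Phase (III.D.4), subjects receive "rizatriptan 10 mg encapsulated tablets or look-alike placebo capsules". Procedures (IV.B) repeats that treatment is double-blind.

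Section III.F gives the handling steps in this order:

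- Active tablets are encapsulated and placebo capsules are made to look alike.
- Then: "All capsules will be labeled with NDC numbers so that active drug and placebo can be identified".
- Randomization codes are entered in the Research Pharmacy record.
- On receipt of a prescription, "drug or placebo will be placed into prescription bottles with required labeling". What the label shows is not specified.
- Before release, pharmacy staff check each prescription against their own record.
- Delivery comes next: "Then the prescription will be dispensed to subjects or mailed to their homes".
- Bottles later come back, empty or not, as a check on what was supplied and taken.
- If questions come up after dispensing, "the research pharmacists will be able to identify study drug for each subject by cross referencing the NDC numbers and randomization codes".

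**The concern.** The shells match, but each one is said to carry a number whose stated purpose is to separate the arms, and those capsules leave the pharmacy. If a reader of the number could tell which product it stood for, matching shells would give no protection.

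The stakes come from who does the rating. The main outcome, 1a(1), is a drop from Grade 3/2 to Grade 1/0 at one hour, entered by the subject in the Vestibular Symptom Diary. Treatment satisfaction and quality of life are also recorded by the subject, at 48 hours. For adverse effects the documents differ: III.D.4 has subjects record them, while III.E item 2 describes the toxicity scale as rated by a clinician. Either way, a person who knew the arm could rate differently. Study personnel also discuss each treated attack with the subject by telephone, so what staff can see matters too.

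**Working it through.** The plan gives no figure on this point, so the check sets the passages side by side.

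**1. Is masking stated?** Yes, for appearance. III.F and III.D.4 both give encapsulated active drug and look-alike placebo. The gap concerns only the NDC number and the bottle label.

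**2. Where is the number, and what is it for?** "All capsules will be labeled with NDC numbers so that active drug and placebo can be identified" places it on the capsule, on every capsule, and gives its purpose as telling the products apart. The sentence does not say for whom.

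**3. Do the numbered capsules reach subjects?** Yes. The next steps are bottling and then "Then the prescription will be dispensed to subjects or mailed to their homes". No step between them covers, removes or neutralises the number.

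**4. Does the bottle label help?** It cannot be judged. III.F asks only for the labeling that is required, without saying what it shows or whether it is the same in both arms.

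**5. Does the pharmacist sentence close the gap?** It names the research pharmacists as able to identify the drug, using the numbers together with codes held in the pharmacy record. It does not say that only they can do so, or that only they see the number. It also describes identification after dispensing, so the link between number and product is meant to stay usable then.

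**6. Does anything elsewhere close it?** The interim analysis (III.J.3, item 7) is to be done without breaking the blind. That presumes an intact blind but does not say what is printed on a capsule. III.E item 3 asks subjects after each dose which treatment they think they took. That may reveal a failed blind later, but it cannot correct ratings already given.

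**7. Scope.** The sentence covers all capsules. With 120 planned subjects at 2:1, that is 120 × 2/3 = 80 on rizatriptan and 120 × 1/3 = 40 on placebo. At one capsule per attack and up to three attacks each, it is at most 120 × 3 = 360 doses.

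**8. Size of bias.** It cannot be derived. It would need the share of subjects or staff who could read the arm from the number, and the shift in ratings that followed. The documents give neither.

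**The case against.** The strongest reply is that III.F can be read consistently with a blinded trial. The NDC sentence follows the manufacturing steps and precedes bottling. The only people named as identifying the drug are pharmacists, who need a second item, the randomization code in their own record. Every design statement requires blinding. On this reading the number is a stock-tracking mark that nobody outside the pharmacy can interpret. The design is also parallel, so a subject never holds a capsule from the other arm to compare. This reply stands to the extent that a pharmacy mark is plausible and a broken blind is not shown. It does not remove the point, because the written procedure still puts the mark on what is dispensed and never says that it is unreadable or the same in both arms.

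Two stronger readings are tempting.

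- A reader might infer that the trial has no masking, or that subjects could look up their arm. The documents state look-alike capsules, and they do not show that an NDC number alone can be decoded.
- A reader might infer that staff could work out the arms from how often each number appears under 2:1 allocation. With one fixed, visible number per arm and simple randomization, the more frequent number would be active drug with probability P(X > n/2), X ~ Binomial(n, 2/3), which is 0.787 for n = 10 and 0.908 for n = 20. The documents do not say that staff see the numbers or that the numbers are constant within an arm, so this is no evidence of unblinding and the conclusion does not use it.

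**Conclusion.** The point holds as a conflict on the literal reading of III.F and an avoidable risk. It does not show that the blind failed. It is more than a missing detail, because a stated rule, arm-identifying numbers on all capsules, works against the double-blind design, and no other statement limits who sees those numbers. It should be corrected.

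The scope is every dispensed capsule in both arms; the effect on any outcome is unknown. The conclusion rests on two things: that the sentence means what it says about the capsules themselves, and that no masking step exists outside these documents. If the numbers were only on bulk stock, or were covered or replaced before dispensing, the matter reduces to wording.

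**What to change.** Amend III.F to say that:

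1. NDC or lot numbers that distinguish the arms appear only on bulk stock and in the Research Pharmacy record.
2. Dispensed capsules and bottle labels do not differ between arms. A subject number in one format for both arms would do; a kit-number system is another workable method but is not essential.
3. The research pharmacy holds the link from that identifier to the product and uses it when bottles are returned or questions arise.

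Since the file ends with a results abstract, the trial report should also state what the dispensed capsules and bottles actually carried.

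The cost is a short edit and a small labelling task, with nothing added for subjects. There is one real loss. Bottles are returned partly to confirm that the right product was supplied, and a filling error could no longer be found by inspecting a returned capsule. Detection would rely on the check against the pharmacy record that III.F already requires before dispensing.
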